#### 12.2 Sample Size Considerations

The planned sample size is 100 subjects, who will be randomly allocated (1:1:1:1) into three treatment groups and one control group. The sample size was chosen empirically, based on sample sizes of other exploratory studies of this general type. This exploratory study is not powered to formally test equivalency or non-inferiority in immunogenicity among groups according to malaria prophylaxis. Subjects who withdraw prior to first vaccination will be replaced by the next enrolled subject who will be assigned to the same group as the withdrawn subject. Replacement subjects will not be randomized.

### 12.2.1 Safety Review

A descriptive summary of adverse events that were reported throughout the trial will be produced.

## 12.3 Final Analysis Plan

## **Primary Objective Analysis**

Descriptive analyses for the primary endpoints will be based on per-protocol analysis data sets using the RFFIT data from blood samples taken 14 days post completion of all four vaccine doses. Separate descriptive analyses will be conducted for each per-protocol data set and group.

## **Secondary Objective Analysis**

Descriptive analyses for the secondary endpoints will be based on per-protocol analysis data sets using the RFFIT data from blood samples taken prior to third and fourth dose of rabies vaccine and 28 days post fourth vaccine dose.

## Per Protocol Analysis Set

The Per-Protocol (PP) analysis set will include all subjects who had no protocol deviations at the time that the data was collected. Two PP analysis sets will be produced for the primary objective that will contain separate data from blood drawn on day 0 and 14 days post 4th vaccination. Descriptive analysis of the secondary endpoint will require three additional per protocol analysis sets for blood drawn prior to 3rd and prior to 4th vaccination and on day 28 post 4th vaccination.

Subjects will be excluded from the PPAS for the following reasons:

- 1. Subject did not meet all protocol-specified inclusion/exclusion criteria or experienced a definitive contraindication
- 2. Administration of vaccine was not done per protocol
- 3. Subject did not receive vaccine in the proper time window as defined in the study procedures
- 4. Subject did not provide a post-dose serology sample in the proper time window as defined in the study procedures\*
- 5. For the malarone and doxycycline groups, subject missed the three or more of the daily dose of antimalarial in any one week.
- 6. For the chloroquine group, subject missed their weekly dose by three or more days

For the computation of GMTs, a titer reported as < LLOQ will be converted to a value of 0.5 LLOQ.

For calculating fold-rise and titer ratio (GMTR), < LLOQ will be converted to 0.5 LLOQ for a numerator and < LLOQ will be converted to LLOQ for a denominator

Any titer reported as > ULOQ (upper limit of quantization) will be converted to ULOQ.

Missing data will not be imputed.

\*Subjects whose serology sample is outside the defined window for the secondary endpoint will still be included in the primary endpoint analysis.

·

Potential outliers will be identified using histograms and modified box plots or normal probability plots, when appropriate. Choice of subsequent tests for outliers (e.g. Grubbs, Tietjen-Moore and ESD) will depend on the number and nature of suspected outliers and may require data transformation. Bootstrapped estimates of standard errors may also be reported. Sensitivity analysis of effect of outliers on descriptive statistics will be conducted, and if necessary descriptive statistics that include and exclude outliers will be reported

#### 13 SOURCE DOCUMENTS AND ACCESS TO SOURCE DATA/DOCUMENTS

Source documents are original documents or certified copies, and include, but are not limited to medical and hospital records, screening logs, informed consent forms, telephone contact logs, and worksheets. The purpose of trial source documents is to document the existence of subjects and to substantiate the integrity of the trial data collected. Investigators must maintain source documents so that they are accurate, complete, legible, and up to date.

The subject screening and enrollment log should list all individuals contacted by the Investigators to participate in the trial, regardless of the outcome.

Source documents will be stored in a secure location with access restricted to study personnel for the protection of confidentiality of subjects.

Study staff will permit authorized representatives of Upstate Medical University and regulatory agencies to examine (and when required by applicable law, to copy) research records for the purposes of quality assurance reviews, audits, and evaluation of the study safety, progress and data validity.

## 14 QUALITY CONTROL AND QUALITY ASSURANCE

# 14.1 Quality Control in Data

Accuracy of data in the database is reviewed on numerous levels. Every attempt is made by the CRC to review source documentation prior to the subject leaving the site. Data is reviewed during data entry, usually completed within 24 hours of the subject visit. Source document to database entry is monitored 100% by the clinical monitor. Any discrepancies between the source and database will be corrected by the CRC.

Product accountability is the responsibility of the principal investigator or designee. Documentation pertaining to product accountability are monitored by the clinical monitor and SUNY-UMU Pharmacy.

## 14.2 Quality Assurance in Clinical Study

During review of a clinical protocol, the SUNY IRB ensures that staff, who will be part of the clinical study, are properly trained to perform the tasks assigned. Additionally, training records are reviewed by the clinical monitor.

The SUNY IRB works very closely with the SUNY Quality Assessment and Improvement Programs (QAIP) which is a post (IRB) approval monitoring program aimed at providing subjects with an extra level of protection by reviewing the conduct of the study in real time. In the event a quality issue arises, the QAIP office will make recommendations for a corrective action and it is the responsibility of the principal investigator to ensure the corrective action has been implemented.

#### 15 PROTECTION OF HUMAN SUBJECTS

#### 15.1 Ethical Standard

The investigator will ensure that this study is conducted in full conformity with the principles set forth in the Declaration of Helsinki (2008) as far as adopted by the concerned regulatory authorities as well as in accordance with 45 CFR Part 46 and/or the ICH E6. The investigator will ensure that this study is conducted in full conformity with the applicable national and local requirements regarding ethical committee review, informed consent, and other statutes or regulations regarding the protection of the rights and welfare of human subjects participating in biomedical research.

#### 15.2 Institutional Review Board

The protocol, informed consent form(s), recruitment materials, and all subject materials will be submitted to the IRB for review and approval. Approval of both the protocol and the consent form must be obtained before any subject is enrolled. Any amendment to the protocol will require review and approval by the IRB before the changes are implemented in the study.

Copies of these approvals, along with information on the type, version number, and date of document, and the date of approval, must be forwarded by the Investigator HRPO.

#### 15.3 Informed Consent Process

Informed consent is a process that is initiated prior to the individual agreeing to participate in the study and continues throughout study participation. Extensive discussion of risks and possible benefits of study participation will be provided to subjects and their families, if applicable. A consent form describing in detail the study procedures and risks will be given to the subject. Consent forms will be IRB-approved, and the subject is required to read and review the document or have the document read to him or her. The investigator or designee will explain the research study to the subject and answer any questions that may arise. The subject will sign the informed consent document prior to any study-related assessments or procedures. Subjects will be given the opportunity to discuss the study with their surrogates or think about it prior to agreeing to participate. They may withdraw consent at any time throughout the course of the study. A copy of the signed informed consent document will be given to subjects for their records. The rights and welfare of the subjects will be protected by emphasizing to them that the quality of their clinical care will not be adversely affected if they decline to participate in this study.

The consent process will be documented in the clinical or research record.

## 15.4 Subject Confidentiality

Subject confidentiality is strictly held in trust by the investigators, study staff, and the sponsor(s) and their agents. This confidentiality is extended to cover testing of biological samples in addition to any study information relating to subjects.

The study protocol, documentation, data, and all other information generated will be held in strict confidence. No information concerning the study or the data will be released to any unauthorized party without prior approval of the Principal Investigator.

The study monitor may inspect all study documents and records required to be maintained by the investigator, including but not limited to, medical records (office, clinic, or hospital) for the study subjects. The clinical study site will permit access to such records.

The IRBs, and regulatory agencies, including the FDA, require direct access to all study records, and will treat these documents in a confidential manner.

## 15.5 Future Use of Stored Specimens and Other Identifiable Data

Any unused part of the research samples will be securely stored at WRAIR or Upstate Medical University for at least 5 years.

Subjects will be asked to indicate on the ICF whether they will permit the future use of any unused samples for other tests. If they refuse permission, the samples will not be used for any testing other than that directly related to this study. If they agree to this use, they will not be paid for giving permission. (Anonymity of samples will be ensured.) The aim of any possible future research is unknown today, and may not be related to this particular study. It may be to improve the knowledge of vaccines or infectious diseases, or to improve laboratory methods. Genetic tests will never be performed on these samples without individual informed consent.

#### 16 DATA HANDLING AND RECORD KEEPING

The investigators are responsible for ensuring the accuracy, completeness, legibility, and timeliness of the data reported. All source documents should be completed in a neat, legible manner to ensure accurate interpretation of data.

At specified intervals, the Investigator or an authorized designee will interview the subjects to collect information, and will attempt to clarify anything that is incomplete or unclear. All clinical trial information gathered by the study site will be reported electronically by the Investigator or authorized designee using a web-based eCRF held at Frontier Science in Amherst, NY. The eCRF has been designed specifically for this trial using a validated Electronic Records / Electronic Signature-compliant platform (21CFR Part 11).

## 16.1 Data Management Responsibilities

Data collection and accurate documentation are the responsibility of the study staff under the supervision of the investigator. All source documents and laboratory reports must be reviewed by the study team and data entry staff, who will ensure that they are accurate and complete. Unanticipated problems and adverse events must be reviewed by the investigator or designee.

Data monitoring at the sites and quality control in the form of computerized logic and / or consistency checks will be systematically applied in order to detect errors or omissions. Any questions pertaining to the reported clinical data will be submitted to the Investigator for resolution using the Electronic Data Capture (EDC) system. Each step of this process will be monitored through the implementation of individual passwords to maintain appropriate database access and to ensure database integrity.

The Investigator is responsible for the timeliness, completeness, and accuracy of the information in the eCRFs; must provide explanations for all missing information; and must sign the eCRF using an e-signature.

## 16.2 Data Capture Methods

Clinical source data will be captured on paper and entered into electronic database by study staff.

Upon completion of training, each user requiring access to the EDC system will be issued a unique username and password. In the event of a change in trial personnel, each newly assigned individual will receive a unique username and password; the username and password of a previous user may not be reissued.

Immunogenicity data will be performed at the laboratory level following the laboratory's procedures. Information from the laboratory will be checked for consistency before integration into the clinical database.

After integration of all corrections in the complete set of data, the database will be released for statistical analysis.

# 16.3 Study Records Retention

The Investigator will retain all source documents, consent forms, for at least 2 years after the investigation is discontinued.

The Investigator will retain all documentation pertaining to the trial. The protocol, documentation, approvals, and all other documents related to the trial, including certificates attesting that satisfactory audit and inspection procedures have been carried out will be kept by Upstate in the Investigator's File. Data on AEs are included in the Investigator's file. Archived data may be held on microfiche or electronic records, provided that a back-up exists and that a hard copy can be obtained if required. All data and documents will be made available if requested by relevant authorities.

#### 16.4 Protocol Deviations

A protocol deviation is any noncompliance with the clinical study protocol, Good Clinical Practice, or Manual of Procedures requirements. The noncompliance may be on the part of the subject, the investigator, or study staff. As a result of deviations, corrective actions are to be developed by the study staff and implemented promptly.

These practices are consistent with investigator and sponsor obligations in ICH E6:

- Compliance with Protocol, Sections 4.5.1, 4.5.2, 4.5.3, and 4.5.4.
- Quality Assurance and Quality Control, Section 5.1.1
- Noncompliance, Sections 5.20.1 and 5.20.2.

All deviations from the protocol must be addressed in study subject source documents and reported to the IRB according to their requirements.

· .

# **APPENDIX A: SCHEDULE OF EVENTS**

GROUP 1 (Chlore		GRO	UP 2	(Malarc	ne), (	ROU	P 3 (De	охусу	cline)		
Study Day	-60 to	0	7	14	17	21	28	31	35	42	56
Visit Type	SCR	BL		BL VAC	BL VAC	BL VAC	BL VAC	BL		BL	BL
Time Windows (days)	-60 to 0	0	+/- 1	+/- 1	+/- 1	+/- 1	+/- 2	+/- 2	+/- 2	+/- 3	+/- 7
Informed Consent IC Review	Х	Х									
Inclusion/Exclusion Criteria	Х	Х									
Medical Records Release	Х										
Contraindications				Х	Х	Х	Х				
Medical History	Х	Х		Х	Х	Х	Х				
Physical Exam	Х										
Targeted Physical Exam a		Х	Х	Х	Х	Х	Х	Х	Х	Х	Х
Vital Signs	Х	Х	Х	Х	Х	Х	Х	Х	Х	Χ	Χ
Urine Pregnancy Test b	Х	Х		Х	Х	Х	Х				
Concomitant Medication	X	Х	Х	Х	Х	Х	Х	Х	Х	Х	Х
Demography	X										
Randomization		Χ									
Confirm Group Assignment c			х	Х	х	Х	Х		Х		
Blood Draw for Research		Х		Х	Х	Х	Х	Х		Х	Х
Collect Urine Group 1		Х	Х	Х		Xe	Xe		Xe	Xe	Xe
Dispense Medication Group 1		Х	Х	X		Х	Х		Х		
Dispense Medication Groups 2 and 3		Х									
Review Medication Groups 2 and 3			Х	Х		Х	Х		Х		

Vaccination				X	X	X	X				
Study Day	-60 to	0	7	14	17	21	28	31	35	42	56
Final Drug Accountability Groups 2 and 3										Х	
AE/SAE		Х	Х	Х	Х	Х	Х	Х	Х	Х	Х
15 min post dose observation d		Х	Х						Х		
30 min post vaccine observation				Х	Х	Х	Х				

a – At Investigator's discretion

b – Female subjects only

c - Confirm group assignment on Day 7 & Day 35 applies to Group 1 only

d – 15 minute observation on Day 7 & Day 35 applies to Group 1 only

e – Urine samples may not be collected at later dates pending results from early samples

# **APPENDIX B: SCHEDULE OF EVENTS**

# **GROUP 4 (Control)**

Study Day	-60 to 0	0	3	7	14	17	28	42
Visit Type	Screening	BL	BL	BL	BL	BL	BL	BL
		VAC	VAC	VAC	VAC			
Time Windows (days)	-60 to 0	0	+/- 1	+/- 1	+/- 1	+/- 2	+/- 3	+/- 7
Informed Consent/IC	Х	Χ						
Review								
Medical Records Release	Х							
Inclusion/Exclusion Criteria	Х							
Contraindications		Χ	Χ	Х	Х			
Medical History	Х	Χ	Χ	Х	Х			
Physical Exam	Х							
Targeted Physical Exam a		Χ	Χ	Х	Х	Х	Х	Х
Vital Signs	Х	Χ	Χ	Х	Х	Х	Х	Х
Urine Pregnancy Test b	Х	Х	Х	Χ	Х			
Concomitant Medication	Х	Х	Х	Χ	Х	Х	Х	Х
Demography	Х							
Randomization		Х						
Blood Draw for Research		Х	Х	Х	Х	Х	Х	Х
Confirm Group Assignment		Х	Х	Х	Х			
Vaccination		Χ	Χ	X	X			
AE/SAE		Χ	Χ	X	X	X	X	Х
30 minute post vaccine		Χ	Χ	Х	X			
observation								

a – At Investigator's discretionb – Female subjects only

## **APPENDIX C: Blood Draw Schedule**

# GROUP 1 (Chloroquine), GROUP 2 (Malarone), GROUP 3 (Doxycycline)

Study Day	0	7	14	17	21	28	31	35	42	56
Serum (8.5 mL)	1		1	1	1	1	1		1	1
PBMC (8.0 mL)			5		3	3			5	5
Daily BV (mL)	8.5	0	48.5	8.5	32.5	32.5	8.5	0	48.5	48.5
CBV (Total)	8.5	8.5	57	65.5	98	130.5	139	139	187.5	236
Total (56 Days)										236

# **GROUP 4 (Control)**

Study Day	0	3	7	14	17	28	42
Serum (8.5 mL)	1	1	1	1	1	1	1
PBMC (8.0)	5		3	3		5	5
Daily BV (mL)	48.5	8.5	32.5	32.5	8.5	48.5	48.5
CBV (Total)	48.5	57	89.5	122	130.5	179	227.5
Total (56 Days)							227.5

STUDY TITLE: Effect of Antimalarial Drugs on the Immune Response to Rabies Vaccine for Post-exposure Prophylaxis. A Randomized, Open Label, Trial in Healthy US Adults Age 18-60 Years

NCT#: 02564471

DOCUMENT DATE: 10 January 2017

Effect of Antimalarial Drugs on the Immune Response to Rabies Vaccine for Post-exposure Prophylaxis

A Randomized, Open Label Trial in Healthy US Adults Ages 18-60 Years

Statistical Analysis Plan (SAP) Version 1.0, Dated 10 Jan 2017

Funder: MILVAX

[name]

Walter Reed Army Institute of Research

[name] [name] 20910

Principle Investigator: [name]

Upstate Medical University [name] Syracuse, NY 13210

Licensed Products: RabAvert® Rabies Vaccine

Chloroquine Malarone Doxycycline

Research Monitor: [name]

Upstate Medical University [name] Syracuse, NY 13210

Study Site/PI Location: Center for Global Health and Translational Science

Upstate Medical University [name] Syracuse, NY 13210

Study Statistician and [name]

SAP Author: Associate Professor, Department of Health and Preventive Medicine

SUNY Upstate Medical University

[name] Syracuse, NY 13210

Statistical Methods

The analysis will be performed under the responsibility of Upstate Medical University in conjunction with the study partners.

This will be a descriptive study to assess immunogenicity of a licensed rabies vaccine using test dosage schedules in the presence of malaria chemoprophylaxis. No formal statistical hypothesis tests will be conducted. Descriptive analyses will be based on the per-protocol analysis sets using the RFFIT data from blood samples taken samples taken from Day 0, prior to vaccination 3, prior to vaccination 4, 14 and 28 days post 4th vaccination. Separate descriptive analyses will be conducted for each per-protocol data set and group.

Exploratory statistical analyses of final data may be conducted, if indicated by the descriptive results. Parametric, non-parametric and resampling (bootstrapping) methods for statistical inference may be used in exploratory analyses, based on data compliance with assumptions of methods. P -values \leq 0.05 will be considered significant and p-values \leq 0.10 will be considered a trend. Confidence intervals will be constructed at α =0.05 and α =0.10. When necessary, p-value corrections for multiple comparisons will be applied.

A descriptive summary of adverse events and serious adverse events that were reported throughout the trial will be produced.

Descriptive and inferential analyses (if any) will be carried out using SAS Version 9.4 (or more recent versions), which is licensed and supplied by SAS Institute, Cary, NC, USA.

Per-Protocol Analysis Set

The Per-Protocol analysis set (PPAS) will include all subjects who had no protocol deviations at the time that the data was collected. Two PP analysis sets will be produced for the primary objective that will contain separate data from blood drawn on day 0 and 14 days post 4th vaccination. Descriptive analysis of the secondary endpoint will require three additional per protocol analysis sets for blood drawn prior to 3rd and prior to 4th vaccination and on day 28 post 4th vaccination.

Subjects will be excluded from the PPAS for the following reasons:

- 1. Subject did not meet all protocol-specified inclusion/exclusion criteria or experienced a definitive contraindication
- 2. Administration of vaccine was not done per protocol
- 3. Subject did not receive vaccine in the proper time window as defined in the study procedures
- 4. Subject did not provide a post-dose serology sample in the proper time window as defined in the study procedures*
- 5. For the malarone and doxycycline groups, subject missed the three or more of the daily dose of antimalarial in any one week.

6. For the chloroquine group, subject missed their weekly dose by three or more days

*Subjects whose serology sample is outside the defined window for the secondary endpoint will still be included in the primary endpoint analysis.

Subjects will be analyzed by the vaccine group to which they were randomized, subject to the exclusion criteria above

Handling of Missing Data and Outliers

For the computation of GMTs, a titer reported as < LLOQ will be converted to a value of 0.5 LLOQ.

For calculating fold-rise and titer ratio (GMTR), < LLOQ will be converted to 0.5 LLOQ for a numerator and < LLOQ will be converted to LLOQ for a denominator

Any titer reported as > ULOQ (upper limit of quantization) will be converted to ULOQ.

Missing data will not be imputed.

Potential outliers will be identified using histograms and modified box plots or normal probability plots, when appropriate. Choice of subsequent tests for outliers (e.g. Grubbs, Tietjen-Moore and ESD) will depend on the number and nature of suspected outliers and may require data transformation. Bootstrapped estimates of standard errors may also be reported. Sensitivity analysis of effect of outliers on descriptive statistics will be conducted, and if necessary descriptive statistics that include and exclude outliers will be reported

Statistical Methods for Baseline Comparisons

Mean (SD) and median (IQR) age at baseline will be computed and descriptively compared across the six groups. Results will be presented in tabular format. Baseline mean (SD) and median (IQR) of all other quantitative demographic variables of interest at baseline will be calculated for each group and the results will be presented in a table.

The number and percentage of males and females per group at baseline will be calculated and results will be presented in tabular format. The number and percentage per group at baseline of all other qualitative demographic variables of interest will be calculated for each group and the results will be presented in tabular format.

Statistical Methods for Subject Disposition

For each group (three prophylaxis and one control), the number and percentage of subjects who received a total of 0, 1, 2, 3 and 4 rabies vaccinations will be reported in tabular format.

For each group, a line listing of subjects who discontinued the study that includes classification of the most serious reason for termination will be produced.

Statistical Methods for Primary Immunogenicity Objectives

Primary Objective: Compare GMT at 14 days post completion of four dose PEP with PCECV in each of the malaria prophylaxis groups with control to determine if a fifth dose of PEP at that point would be of any added value.

Immunogenicity against rabies will be assessed descriptively using the following parameters:

Timepoints: At 14 days post-completion of four doses of rabies vaccine

 Geometric mean titer (GMT) against rabies virus for the prophylaxis and control groups at 14 days after completion of four doses of vaccine.

A table that presents the total number of per-protocol subjects and GMT against rabies at 14 days post completion of four doses of vaccine by group will be produced.

Statistical Methods for Secondary Immunogenicity Objectives

Secondary Objective: To evaluate GMT over protective titer prior to third dose, fourth dose and 28 days post fourth dose of PCECV.

Immunogenicity will be assessed descriptively using the following parameters:

Timepoints: prior to third and fourth dose of rabies vaccine and 28 days after fourth dose of vaccine

A table that presents, by group, the total number of per protocol subjects and the GMT against rabies prior to the third and fourth dose of vaccine and 28 days after fourth dose of vaccine will be produced.

Statistical Methods for Adverse Events and Serious Adverse Events

For each treatment group, a line listing by subject that describes adverse events and post-baseline day of occurrence of the AE will be produced.

The number and percent of subjects in each group who reported any AE between Days 0 and 372 will be summarized in tabular format.

A table showing the number and percentage of subjects in each group who reported adverse events by general type (category) of event will be produced.

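### Every planned GMT table is per-protocol only, although selection into that set can differ between the drug groups and control and its definition contradicts itself

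*SAP*

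**What the plan says.** SAP, Statistical Methods: "Descriptive analyses will be based on the per-protocol analysis sets using the RFFIT data". The primary and secondary immunogenicity sections each plan one table, giving the number of per-protocol subjects and the GMT by group. Protocol 12.3 agrees. Neither document defines a wider immunogenicity set, missing titres are not imputed, and the only sensitivity analysis planned concerns outliers.

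SAP, Per-Protocol Analysis Set, opens with "The Per-Protocol analysis set (PPAS) will include all subjects who had no protocol deviations at the time that the data was collected". Protocol 12.3 has the same rule: "The Per-Protocol (PP) analysis set will include all subjects who had no protocol deviations at the time that the data was collected". Protocol 16.4 defines a deviation as noncompliance of any kind, by the subject, the investigator or staff. The SAP then says "Subjects will be excluded from the PPAS for the following reasons" and lists six. Reasons 1-4 (eligibility, vaccine administration, vaccine window, serology window) apply to every group. Reason 5 is "For the malarone and doxycycline groups, subject missed the three or more of the daily dose of antimalarial in any one week" and reason 6 is "For the chloroquine group, subject missed their weekly dose by three or more days". A footnote adds "Subjects whose serology sample is outside the defined window for the secondary endpoint will still be included in the primary endpoint analysis".

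Protocol 5.4.1 and 12.2 replace anyone who withdraws before first vaccination with the next enrolled subject, who is placed in the same group without randomisation. The SAP does not mention replacements and says "Subjects will be analyzed by the vaccine group to which they were randomized".

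**The concern.** The primary objective compares each drug group with a randomised control to judge whether a fifth dose adds value. Exploratory p-values and confidence intervals are allowed, and the proteomic and cellular assays may depend on whether a GMT difference is seen. If subjects leave the analysis for reasons that exist only in the drug groups, part of an observed difference, or of its absence, could reflect who was kept. With no GMT outside the per-protocol set, a reader could not tell.

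The wording adds a second problem. Two analysts working from the same text could build different primary datasets, and the choice between them could be made after titres are known.

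**Working it through.** **Which groups each filter can reach**

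- Reasons 5-6: Groups 1-3 only, because controls take no antimalarial.
- Within Groups 1-3, mainly Groups 2 and 3. They take the first of 42 doses at the Day 0 visit and the other 41 unobserved (Protocol 6.1.2, 6.5). Chloroquine is directly observed (6.3). Its Day 14, 21 and 28 doses fall on vaccination visits with windows of 1-2 days, so a visit three or more days off already triggers reason 3. Reason 6 adds little beyond Days 7 and 35.
- Replacement: controls are vaccinated at the Day 0 visit, Groups 1-3 on Day 14 after two weeks on drug. Withdrawal before first vaccination can hardly occur in Group 4.

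**The two readings of the definition**

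The opening sentence, read with Protocol 16.4, excludes after one missed tablet. Reason 5 excludes only at three or more in a week. The footnote keeps subjects with an out-of-window pre-dose sample, whom the opening sentence would drop. This is small in practice, since those samples are drawn at vaccination visits where reason 3 would usually apply. It does not arise for the sample 28 days after dose 4, which comes after the primary one.

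**How far the readings differ in a daily-drug group**

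The documents give no adherence rate, so per-dose adherence q is an assumption. With 25 subjects and independent misses:

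- Literal sentence: 25 × q^41.
- List, fixed weeks: 25 × P(≤2 missed of 6) × P(≤2 missed of 7)^5. At q = 0.95 this is 25 × 0.9978 × 0.9962^5 = 24.5.
- List, any 7 consecutive days: exact Markov chain over the 41 doses.

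Where adherence varies between subjects, q follows a beta distribution with a+b = 5 to 10; the literal rule becomes 25 × B(a+41, b)/B(a, b).

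| Mean adherence | Misses | Literal | List, fixed weeks | List, any 7 days |
|---|---|---|---|---|
| 95% | independent | 3.1 | 24.5 | 23.8 |
| 97% | independent | 7.2 | 24.9 | 24.7 |
| 99% | independent | 16.6 | 25.0 | 25.0 |
| 95% | varying | 10.7-13.9 | 22.6-22.9 | 21.7-21.9 |
| 97% | varying | 15.1-17.6 | 23.6-23.9 | 23.1-23.3 |
| 99% | varying | 21.1-22.3 | 24.6-24.7 | 24.4-24.5 |

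With varying adherence the readings differ by 7.8-12.2, 5.5-8.8 and 2.1-3.6 subjects per group. The meaning of a week also matters: the list excludes 2.1% (fixed) or 4.9% (any 7 days) at 95% independent adherence, and 13.6% or 26.4% at 90%.

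**Possible shift in a GMT under the list**

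If a fraction f is excluded and their titres differ 2-fold (assumed), the all-subject and per-protocol GMTs differ by 2^f, in either direction: 1.01 at f = 0.02, 1.04 at 0.05, 1.10 at 0.136, 1.20 at 0.264.

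**Sampling error for comparison**

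The 95% confidence factor for a GMT ratio is 10^(t × SD × √(1/n1 + 1/n2)). With an assumed log10 SD of 0.3-0.5 and 25 v 25 (t = 2.011), it is 1.48-1.92.

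**Replacements**

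If a share w withdraws before vaccination (assumed), 75w of the 75 vaccinated antimalarial subjects are replacements: 3.75, 7.5 or 15 at 5%, 10% or 20%, which is about 1-5 per group. Leaving out five from a group (20 v 25) widens the factor only to 1.52-2.01.

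**The case against.** The trial is declared descriptive and exploratory, with no formal tests and no power claim. A per-protocol analysis suits the question in Protocol 2.2, which is about compliant soldiers. Ordinary reading lets a specific list govern a general sentence; otherwise reasons 5-6 and the footnote have no purpose. Protocol 6.3 expects unused tablets to be returned and recorded. Under the list, few subjects are lost at good adherence. The group of a replacement is already fixed by Protocol 5.4.1. The number of per-protocol subjects, the table of 0-4 vaccinations and the discontinuation listing show part of the attrition, and optional exploratory analyses are not expressly limited to the per-protocol set.

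Most of this stands, and it sets the size of the point. A reader might infer that most daily-drug subjects would be dropped. That needs both an assumed adherence and a reading that is probably not intended. A reader might infer that the primary result is biased, or that the per-protocol set should give way to another. The documents give no basis for a direction or an amount, and the set fits the question. A reader might also infer that replacements have no analysis group; the protocol assigns them one, and the SAP wording is merely loose.

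The objection does not meet three facts. No wider GMT is committed to, exclusions by reason are not tabulated, and neither document says that the list overrides the opening sentence.

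**Conclusion.** The point holds as one of transparency and of an analysis set that needs settling before titres are examined. All planned GMT comparisons use a set from which adherence can remove subjects in the drug groups but not in control, and nothing planned shows the effect. The asymmetry sits mainly in the Malarone and doxycycline groups, and much less in chloroquine. The definition contradicts itself as written.

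On the assumptions above the bias is modest: about 1.01- to 1.10-fold for 2-14% excluded, and 1.20-fold at 90% adherence with the any-7-days reading, against sampling error of 1.48- to 1.92-fold. Direction is unknown, and no upper bound is claimed because adherence, titre SD and titre differences are all assumed. The replacement issue is mainly clarification. The change is worth making because it is nearly free and removes a choice that could otherwise be made after the data are seen.

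**What to change.** (a) Keep the per-protocol analysis. Beside it, report GMTs and GMT ratios v control, by assigned group, for all vaccinated subjects with a titre at the nominal visit, regardless of adherence, sample window or number of doses received. For the primary endpoint the nominal visit is Day 42 in Groups 1-3 and Day 28 in Group 4. Show how many had fewer than four doses. This column will mainly add less adherent or out-of-window completers. It will recover few withdrawals, because Protocol 5.5.2 provides blood after a safety withdrawal only within two weeks of the last vaccination.

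(b) In the SAP and Protocol 12.3, replace the opening sentence so that the six listed reasons alone define the per-protocol set. State whether the week in reason 5 is a fixed study week or any 7 consecutive days. Tabulate exclusions by group and reason.

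(c) As a minor addition, state that replacements are analysed by assigned group, flag them, and show the primary comparison without them as a sensitivity row. Note that this discloses the 14-day run-in filter in Groups 1-3 but does not remove it.

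Cost: wording in two documents, one extra column in the GMT tables, one exclusion table and one sensitivity row. It needs no new data and no change to enrolment or to the replacement procedure.
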